### 2.2. Intended purpose

The intended purpose of corpulse1 & 3 defibrillators in cardiac arrest is to terminate VT or VF with external defibrillation in order to restore spontaneous circulation. This can be done by electrodes placed in standard A-L position, but in some circumstances also A-P position (see above). I.e. using one defibrillator in with either electrode position (A-L or A-P) are within the scope of the CE-mark of the investigational devices. This is all part of standard clinical practice and within the intended use of the investigational device.

An alternative strategy is to use two defibrillators (both A-L and A-P electrode position) and to perform two defibrillations in rapid sequence, approximately 1 second apart, so called double sequential defibrillation (DSD). This strategy is, at least partially, outside the CE-mark.

The intended purpose of the investigational device in this clinical pilot trial is to terminate VT/VF by performing DSD as early as possible after the first defibrillation. To our knowledge this is the first clinical trial evaluating an early DSD strategy in cardiac arrest.

#### Performing DSD within the Double-D trial:

In this trial all patients will be connected to corpuls3 with electrodes in standard A - L electrode position.

If another defibrillator (AED) is already attached to the patient at EMS arrival the EMS will remove the electrodes from the other defibrillator and attach cor-patch electrodes in standard A-L position and connect them to corpuls3 in all cases. This is all part of current routine practice.

If randomized to intervention, electrodes from a second defibrillator (corpuls3 or corpuls1) are placed in the anterior-posterior position during interruptions in chest compressions for ventilation, thus not interfering with the electrodes from the first defibrillator. Attachment of the second defibrillator electrodes shall be made as soon as possible after randomization.

Version No: 1.1

Date: 2024-10-27 17 (48)

If the patient has VT/VF at the subsequent rhythm analysis (every two minutes during CPR) both defibrillators are charged simultaneously during chest compressions and shocks from the two defibrillators are delivered with approximately 1 second delay from each other (A-L first, A -P second when possible) and CPR immediately resumed (DSD strategy). For all consecutive defibrillations a DSD strategy will be used if the patient remains in VT/VF, termination of resuscitation or decision to transfer the patient to hospital. The total shock pause (hands off interval where no compressions are performed) is recommended to be less than 5 seconds.

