**Study rationale:** In order to evaluate if an early DSD-strategy could benefit all patients with VT/VF after the first shock, including those not in refractory VF the Double D trial is designed. The first phase of the Double D trial is a pilot-study assessing feasibility and defibrillation safety, presented here. If DSD would prove to be superior to standard defibrillation in a broader cardiac arrest population, also among those not in refractory VF, this would have a large impact on how Advanced Cardiac Life Support (ACLS) should be performed.

**Design:** This is an academic, investigator initiated, openlabel pilot study with a randomized controlled trial (RCT) design and 3:1 allocation (3 DSD: 1 standard). Screening for inclusion will be performed in all cardiac arrests by participating EMS units where there are two study-specific defibrillators available on site (One (1) Corpuls3 + one (1) Corpuls3).

**Study population:** All OHCA patients (≥18 years) with VT/VF at rhythm analysis, at least one defibrillation performed in standard A-L position.

**P:** Adult patients, 18 years or older, with OHCA and a shockable rhythm (VT/VF) after ambulance arrival and at least one defibrillation in standard position

**I:** Application of a second defibrillator with pad-placement in the anterior-posterior (A-P) position as early as possible after the first shock and a double sequential defibrillation in the following rhythm analysis phase if the patient is still in VT/VF

**C:** Standard defibrillation electrode placement (A-L)

**O**: Assessment of feasibility in terms of inclusion, time to inclusion and randomization, adherence to protocol and safety in terms of adverse events and CPR quality.

The pilot study is conducted in the prehospital emergency medical services, i.e. ambulance organizations primary in Alingsås/Kungälv, Sahlgrenska, Gothenburg and Region Halland. Other areas/regions can be allocated later.

Version No: 1.1

Date: 2024-10-27 11 (48)

	The trial will be conducted by participating ambulance units attending OHCA's. These units will perform screening for inclusion, randomization, intervention or control treatment and initial follow up.
Investigational device:	Corpuls3
Number of subjects:	40
Inclusion criteria:	- OHCA patients with VT/VF and at least one (1) defibrillation performed in standard (A-L) position

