# 2. Identification and description of the investigational device

## 2.1. Description of the investigational device

Corpuls3 and Corpuls1 are defibrillators with capabilities of monitoring of cardiac rhythm and vital functions but also defibrillation, cardioversion and pacing and are part of the standard equipment in the EMS units in the participating sites.

Corpuls3 is a portable device with a modular structure which can be used as a defibrillator/monitor or as a full patient monitor in its own right.

The risk classification of Corpuls3 and Corpuls1 are non-invasive IIb

Version No: 1.1

Date: 2024-10-27 13 (48)

Image: Corpuls3

The corpuls3 provides monitoring of cardiac rhythm and vital functions, diagnostic and therapeutic functions for treatment of emergency and intensive-care patients. A 12 lead ECG function allows the user a comprehensive ECG diagnosis, which can be optionally supplemented by ECG analysis software.

[figure not shown]
Further monitoring functions include oxygen saturation measurement (pulse oximetry), carbon dioxide measurement (capnometry) and temperature measurement, in addition to non-invasive and invasive blood pressure monitoring. Corpuls3 provides the following therapeutic functions:

- defibrillation
- cardioversion
- pacing

Defibrillation with corpuls3 is performed with a Biphasic, positive rectangular waveform 4 msec. (90 % energy) and a negative rectangular waveform 3 msec. (10 % energy) pulse.

Version No: 1.1

Date: 2024-10-27 14 (48)

The defibrillator which operates with the corpuls 3-specific biphasic pulse has two operating modes:

- automatic external defibrillation (AED mode)
- manual defibrillation and cardioversion (manual mode)

In AED mode, the user is assisted by an automated ECG analysis, verbal instructions (configurable) and a metronome (configurable). The defibrillation pulse is triggered by the user.

In manual defibrillation mode, the user has full freedom of action and decision-making. Defibrillation is performed by applying disposable adhesive electrodes, so-called corPatch electrodes.

The standard position of the corPatch electrodes is the A-L Position, but alternative electrode positioning, including A-P should be considered in refractory VF since 2015.

[figure not shown]

Image Anteriolatal (standard) corpatch electrode placement from corpuls3 user manual

Version No: 1.1

Date: 2024-10-27 15 (48)

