#### In summary:

- First defibrillator (corpuls3) is attached in A-L position.
- Second defibrillator (corpuls3) is attached in A-P position.
- Both defibrillators are set in manual mode
- If VT/VF at next rhythm analysis, chest compressions are resumed and both defibrillators are charged to maximal energy (200J Biphasic for Corpuls3)
- Defibrillations are performed sequential (approximately 1s apart), preferably A-L first, A-P second

If randomized to the control group, the ambulance crew team will continue Advanced Cardiac Life Support (ALS) in accordance with standard of care. Defibrillation is performed with standard electrode placement using one corpuls3 defibrillator.

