# 3.2. Evaluation of results of prior testing, assessments and clinical investigations

As stated above, DSD has already been tested in a previous randomize controlled trial in humans and may according to international guidelines be considered in refractory VT/VF. The difference in this trial is to apply DSD after one failed defibrillation, before the VT/VF is considered refractory.

DSD with Corpuls3 is considered to be technically safe according to manufacturer, please see attached file "231130\_DSED\_eng\_Corpuls". Currently, corpuls3 and corpuls1 are tested for combability and technical safety when used for DSD.

Before those results are final and an application for a substantial modification is approved by the Swedish Ethical Review Authority and the Swedish Medical Products Agency no combination of corpuls3 and corpuls1 will be used in this trial.

Version No: 1.1

Date: 2024-10-27 21 (48)

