## 4.5. Steps to be taken to control or mitigate risks

- 1. Ambulance crew training. As mentioned above the main risk with the DSD strategy, as far as we know, is connected with the application of defibrillation electrodes and defibrillation. Therefore, all participating ambulance units must be trained and certified before participation in the trial. This in order to minimize risk of long interruptions in chest compressions and correct electrode placement.
- 2. Close monitoring will be done by the sponsor and the monitoring team on a case to case base. During the pilot study individual assessment and early feed-back of EMS intervention for every included patient can allow the sponsor for early detection of unanticipated adverse events. Please see also attached monitoring plan
- 3. Evaluation of defibrillators after each and every use. The corpuls3 performs a complete system check each time it is switched on. This internal automatic self-test checks the system components.

If error messages appear during automatic self-test, these are displayed in the

Version No: 1.1

Date: 2024-10-27 23 (48)

status line and listed in the event history. After each use of DSD, the defibrillators will be checked for malfunction by performing an automatic self-test to ensure functionality.

Furthermore, all defibrillators used in this DD study will be tested using a test-box and performing a test discharge will be performed once weekly during the study period (part of current routine) and as soon as possible after each DSD use.

- 4. Stepwise escalation of the pilot phase will be done in order to uncover unknown risks. In order to perform close monitoring of all included patients and feed-back from participating ambulance crew the trial will have an escalation strategy within the pilot study starting in two ambulance organizations and then escalate. The training protocol can be modified during the pilot study to mitigate potential risks. For all significant modifications, the Swedish medical product agency and the Swedish Ethical Review Authority will be notified. Please see also 9. Amendments to CIP.
- 5. Testing of combability of corpuls3 devices (performed) and for corpuls3 and corpuls1 (ongoing). Before those results are final and an application for a substantial modification is approved by the Swedish Ethical Review Authority and the Swedish Medical Products Agency no combination of corpuls3 and corpuls1 will be used in this trial.

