## 6. Design of the clinical investigation

#### 6.1. General information

**Design:** This is an academic, investigator initiated, open-label pilot study with a randomized controlled trial (RCT) design and 3:1 allocation (3 DSD: 1 standard). Screening for inclusion will be performed in all cardiac arrests by participating EMS units where there are two study-specific defibrillators available on site (One (1) Corpuls3 + one (1) Corpuls3 *or* one (1) Corpuls1).

**Study population:** All adult OHCA patients (≥18 years) with VT/VF at rhythm analysis after the first defibrillation.

Version No: 1.1

Date: 2024-10-27 25 (48)

**Study setting:** The study is conducted in the prehospital emergency medical services, i.e. ambulance organizations. The trial will be conducted by participating ambulance units attending OHCA's staffed with special nurses. These units will perform screening for inclusion, randomization, intervention or control treatment and initial follow-up. All ambulance units in Sweden follow European resuscitation council (ERC) guidelines published in 2021 [4] and perform team training on an annual basis for high quality provision of ACLS care in OHCA.

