#### Defibrillator requirements:

In this study all participating EMS units will have corpuls3 defibrillators.

A perquisite for inclusion in this trial is that there are two study specific defibrillators on site, this means that either one EMS unit with two defibrillators (corpuls3) or two EMS units on site with one corpuls3 each.

In situations where the first EMS unit only has one defibrillator, but a second EMS unit arrives the patient can still be included as soon as the second defibrillator is on site. Therefore, in clinical practice the inclusion of patients will follow the flow-chart above.

If there is another defibrillator attached to the patient at EMS arrival (a public access AED or a AED from fire-fighters or police) that AED will be removed and the corpatch electrodes from

Version No: 1.1

Date: 2024-10-27 29 (48)

corpuls3 will be attached to the patient and connected to corpuls3 in all cases (this is in accordance with routine practice).

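### Sections 2.2 and 6.1 admit a Corpuls1 as second defibrillator without condition, although 3.2 and 4.5 bar that pair for now

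*Protocol*

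**What the plan says.** Two places let the second defibrillator be a Corpuls1:

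- Section 2.2, under the account of how DSD is performed, instructs that in the intervention arm "electrodes from a second defibrillator (corpuls3 or corpuls1) are placed in the anterior-posterior position".
- Section 6.1 makes screening depend on two study defibrillators being on site, which it specifies as "One (1) Corpuls3 + one (1) Corpuls3 *or* one (1) Corpuls1".

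Two places bar the mixed pair for the time being:

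- Section 3.2 states that "no combination of corpuls3 and corpuls1 will be used in this trial" until the test results are final and both the ethics authority and the medical products agency have approved a substantial modification.
- Section 4.5, item 5, repeats this as a risk-mitigation step and gives the status of the work: "Testing of combability of corpuls3 devices (performed) and for corpuls3 and corpuls1 (ongoing" (the parenthesis closes there).

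Three places name Corpuls3 only:

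- Synopsis, Design: "two study-specific defibrillators available on site (One (1) Corpuls3 + one (1) Corpuls3".
- Section 2.2, summary list: "Second defibrillator (corpuls3) is attached in A-P position".
- Section 6.6, Defibrillator requirements: "either one EMS unit with two defibrillators (corpuls3) or two EMS units on site with one corpuls3 each".

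On availability, section 2.1 says of the Corpuls3 and Corpuls1 together that they "are part of the standard equipment in the EMS units in the participating sites". The funding section has the sponsor supplying additional Corpuls1 units and gives no date.

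**The concern.** The restriction on the mixed pair is one of the protocol's listed risk controls, and it exists because the technical compatibility of the two models under DSD has not yet been shown. The manufacturer's safety statement cited in 3.2 covers DSD with Corpuls3. Section 2.2 says that DSD lies at least partly outside the CE mark, and section 6.2.1 makes defibrillator malfunction a main safety endpoint.

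The two permissive phrases stand in text that directs conduct: 6.1 decides which scenes are screened, and 2.2 describes what is done to the patient. A crew or site relying on either alone could screen with, or deliver shocks from, a pair that the protocol elsewhere forbids. The case-by-case review in 4.5 (item 2) would find this only after the patient had been treated. Section 10 allows no deviation outside emergencies, so sites need a single rule. As written, the same act follows 2.2 and breaches 3.2.

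**Working it through.** No sample size, power or event figure is involved, so the check is a comparison of every place that names the second device or the required pair.

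| Place in the protocol | Second device allowed | Condition stated there |
|---|---|---|
| 2.2, DSD procedure | Corpuls3 or Corpuls1 | none |
| 6.1, Design | Corpuls3 or Corpuls1 | none |
| 3.2 | mixed pair barred | until results are final and modification approved |
| 4.5, item 5 | mixed pair barred | same |
| Synopsis, Design | Corpuls3 | not applicable |
| 2.2, summary list | Corpuls3 | not applicable |
| 6.6, Defibrillator requirements | Corpuls3 | not applicable |

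**Step 1. Is a Corpuls1 as second device necessarily the barred pair?** Yes. Section 2.2 has all patients connected to a Corpuls3 in the A-L position first, and replaces any other defibrillator already attached. Adding a Corpuls1 therefore always gives a Corpuls3/Corpuls1 combination.

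**Step 2. Is the bar in force in this version?** Yes. It lifts only when the test results are final and the modification is approved. Section 4.5 (item 5) reports the mixed-pair testing as ongoing, and the protocol reports no approval.

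**Step 3. Do the two permissive phrases carry the condition or point to it?** No. Neither mentions testing or approval, and neither refers to 3.2 or 4.5.

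**Step 4. Does the protocol say which text prevails?** No order of precedence is stated in the document shown.

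**Step 5. Count.** Places admitting Corpuls1 without condition: 2. Places pointing the other way: 2 that bar the pair + 3 that name Corpuls3 only = 5. Section 2.2 is on both sides of the count, because its procedure text and its summary list disagree. The Design paragraphs of the synopsis and of 6.1 are otherwise close to identical, and only 6.1 adds the Corpuls1 alternative. That is consistent with wording left unaligned, though the document does not say how it arose.

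**Step 6. Could a Corpuls1 be on scene?** It cannot be excluded. Section 2.1 treats both models as standard equipment at the sites, and the sponsor is to supply more Corpuls1 units. The evidence is mixed, because the funding section names only the Corpuls3 as sites' standard equipment. The document gives no basis for estimating how many patients might be affected, so no estimate is made.

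**The case against.** The strongest reply is that the document already settles the matter. The bar is explicit, given twice, and covers the whole trial. A specific, time-limited prohibition can sit beside a general description of the devices eventually intended, so 2.2 and 6.1 may simply anticipate the planned modification. Section 6.2 sends the reader to 6.6 for both the intervention and the comparator, and 6.6 sets the prerequisite for inclusion in Corpuls3 terms only. The summary list in 2.2 follows closely on the loose phrase, names a Corpuls3, and gives a charge energy for that model alone. Crews are also prepared by other means: a compulsory web course requiring full marks, supervised practical training, certification before participation (2.6 and 4.5, item 1), and written sponsor instructions (section 11).

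Much of this stands. It lowers the chance of misuse, and it confirms that the predominant message is Corpuls3 only. It does not remove the conflict. Neither phrase says that it anticipates an approval, and section 3.2 makes that approval a precondition, so this wording belongs in the modified version. The training content described in 2.6 states no Corpuls3-only restriction, and the course material and written instructions are not available to show whether they do. That 6.6 is correct is a reason to limit the repair to two phrases, not a reason to leave them.

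**Conclusion.** The point holds: the wording in 2.2 and 6.1 is wrong as it stands in version 1.1, because it admits without condition a device pair that 3.2 and 4.5 (item 5) currently forbid. Confidence is high, since the conclusion rests on the text alone.

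Its size is limited. Two phrases are at fault, the governing intention is recoverable from the rest of the document, and the planned 40 patients, the endpoints and the analysis are untouched. It should be corrected because it weakens a listed risk control tied to a main safety endpoint. There is no evidence that the pair has been or will be used. The conclusion assumes that no precedence rule exists elsewhere and that the mixed-pair approval had not been obtained when this version was issued; nothing in the protocol suggests otherwise on either point.

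**What to change.** In the DSD procedure text of 2.2 and in the Design paragraph of 6.1, do one of two things:

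1. Delete the Corpuls1 alternative now, and restore it through the substantial modification once that is approved.
2. Keep it, but add to each phrase that a Corpuls1 may be used only after final compatibility results and approval of the substantial modification, with a reference to 3.2 and 4.5.

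The first is cleaner, because it leaves one rule for crews throughout. The synopsis, the summary list in 2.2, the model list in 2.4 and section 6.6 need no change. The cost is two phrases in the next protocol version.

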#### In summary:

- First defibrillator (corpuls3) is attached in A-L position.
- Second defibrillator (corpuls3) is attached in A-P position.
- Both defibrillators are set in manual mode
- If VT/VF at next rhythm analysis, chest compressions are resumed and both defibrillators are charged to maximal energy (200J Biphasic for Corpuls3)
- Defibrillations are performed sequential (approximately 1s apart), preferably A-L first, A-P second

If randomized to the control group, the ambulance crew team will continue Advanced Cardiac Life Support (ALS) in accordance with standard of care. Defibrillation is performed with standard electrode placement using one corpuls3 defibrillator.

## 2.4. Model/type

- Corpuls3
- Corpuls1

## 2.5. Target population

Target population for defibrillation are patients with OHCA and VT/VF after one defibrillation in standard position. The defibrillators deliver energy through corpatch eletrodes attached to the patient in A-L or A-P position. Defibrillation with Corpuls3 and corpuls1 are complianent with relevant GSPR, please see attached files.

## 2.6. Summary of required training/experience needed

Version No: 1.1

Date: 2024-10-27 18 (48)

Corpuls3 may only be operated by trained medical staff of for example hospitals, doctor's offices and emergency medical services, as well as of authorities and public safety organizations. The qualified staff must be:

- trained in proper handling, use and operation of the device and of the approved accessories as well as be
- trained in basic and advanced resuscitator measures (Basic Life Support and Advanced Cardiac Life Support).

All EMS units in this trial provide ACLS care for OHCA and are trained in ACLS. In addition to this all EMS organizations included in the study ensure that EMS-crews are trained in the Double defibrillation strategy prior to participating in the trial.

This is in practice done by:

- a) "Theoretical study concept course". All EMS-crews take a 20-minutes obligatory web-course providing theory and methodology for the study and the intervention. Participants shall reach 100% correct answers in order to be certified as Double D-users.
- b) Practical training. All EMS-crews shall under the supervision of an ACLS-instructor (A-HLR) certified by the Swedish resuscitation council undergo practical training. This training includes application of defibrillation pads in the anterio-posterior position while making sure to minimize interruptions in chest compressions, performing defibrillation in manual mode and charging and defibrillating with two defibrillators in a sequential manner. Special attention during this training to delayed (sequential) defibrillation will be done. All participants shall in front of an instructor demonstrate correct practical performance. Finally, to perform ACLS scenarios with team training using the Double-D-algorithm during ongoing CPR.

These scenarios shall facilitate the early provision of a DSD with maintained safety for all personnel, while minimizing interruptions in chest compressions. All EMS-crews will rehearse the CPR training including DSD training once a year.

